IGA-BP Investigator Global Assessment of Bullous Pemphigoid

IMP Investigational medicinal product

IM intramuscular

IRR Injection-related reaction
ISR Injection site reaction

IV intravenous

IVIg immunoglobulins given intravenously

LRV Lower reference value

MedDRA Medical Dictionary for Regulatory Activities

MMRM Mixed model for repeated measurements

NAb Neutralizing antibody

ARGX-113-2009 Final and Interim Analysis Final 4.0 of 04NOV2024

NCOD Normalized cumulative OCS dose

Pharmacokinetics

NCI National Cancer Institute
NRS Numerical Rating Scale

OCS Oral corticosteroid
OLE Open-label extension
PD Pharmacodynamics

PBO Placebo

PK

PR Partial Remission

PRO participant-reported outcome

PT preferred term QoL Quality of life

QTc corrected QT interval

QTcF Fridericia's corrected QT interval

rHuPH20 recombinant human hyaluronidase PH20

SAE Serious Adverse Event

SAF Safety analysis set

SAP Statistical analysis plan SBP Systolic blood pressure

SC Subcutaneous

SCR all screened participants analysis set

SD Standard deviation

SE Standard error

SGS CR SGS Clinical Research

SOC system organ class

SOP Standard operating procedure

STAT Statistics

TEAE Treatment-emergent adverse event

TCS Topical corticosteroid

TV Target value

WI Work instruction

WHODD World Health Organization Drug Dictionary

SGS	Statistical Analysis Plan	
ARGX-113-2009	Final and Interim Analysis	Final 4.0 of 04NOV2024

DEFINITION OF TERMS

case report form (CRF)	A printed, optical, or electronic document in which protocol required information is recorded for each study participant.
Complete remission (CR)	The absence of new lesions, complete healing of existing lesions, and absence of pruritus.
Complete remission on minimal OCS therapy (CRmin)	Being in CR for \geq 8 weeks and have been on minimal OCS therapy (\leq 0.10 mg/kg/day of prednisone or an equivalent dose of another OCS) for \geq 8 weeks
Complete remission off OCS therapy (CRoff)	Being in CR for ≥ 8 weeks and have been off OCS therapy for ≥ 8 weeks.
Control of disease activity (CDA)	The point at which new lesions cease to form and established lesions begin to heal, and pruritic symptoms start to abate.
Display	Analysis table, figure or listing.
Minimal OCS therapy	An oral prednisone dosage of \leq 0.10 mg/kg/day (or an equivalent dose of another OCS).
Phase	Interval of time in the planned conduct of a study that is associated with a specific purpose: for example, screening, treatment, follow-up.
IMP	Pharmaceutical form of an active ingredient or placebo, being tested or used as a reference in a clinical study.
Partial remission (PR)	The presence of only new transient lesions.
Relapse	Appearance of 3 or more new lesions a month (blisters, eczematous lesions, or urticarial plaques),

SGS	Statistical Analysis Plan	
ARGX-113-2009	Final and Interim Analysis	Final 4.0 of 04NOV2024

or at least 1 large (>10 cm diameter) eczematous lesion or urticarial plaque that does not heal within 1 week, or extension of established lesions or daily pruritus in a participant who has achieved CDA

Transient lesions New lesions that heal within 1 week or pruritus lasting less

than 1 week.

Treatment failure The absence of CDA after being administered oral prednisone at 0.75 mg/kg/day (or equivalent OCS)

for 3 weeks. The investigator has the option to add a fourth week of therapy with oral prednisone 0.75 or 1 mg/kg/day (or equivalent) (based on clinical judgment) before

declaring treatment failure

Treatment-emergent abnormality

Any post-baseline abnormality that was not present at baseline (e.g., hemoglobin normal at baseline and grade 1 post-baseline; glucose low at baseline and high post-baseline; QTcF]450; 480] ms at baseline and >500 ms post-baseline).

ARGX-113-2009 Final and Interim Analysis

Final 4.0 of 04NOV2024

TABLE OF CONTENTS

0	1 0		
Pro	tocol histor	у	3
List	of abbrevi	ations	4
		erms	
Tab		nts	
1.		on	
1.1	Study	objectives	15
	1.1.1	Part A	15
	1.1.2	Part B	16
1.2	Study	design	17
1.3	Expect	red sample size	17
1.4	Interin	analysis	18
	1.4.1	Futility analysis	18
	1.4.1.1	Endpoint used for the futility analysis	18
	1.4.1.2	Missing data imputation	18
	1.4.1.3	Statistical analysis	19
	1.4.1.4	Futility analysis recommendation algorithm	19
	1.4.2	Sample size re-adjustment	20
	1.4.2.1	Statistical calculation	20
	1.4.2.2	Sample size re-assessment algorithm	21
	1.4.3	Control of the type I error for key secondary endpoints	21
	1.4.3.1	Statistical analysis	21
	1.4.3.2 secondary	Algorithm to adapt the methodology to control type I error for key rendpoints	22
	1.4.4	Data access plan	22
	1.4.4.1	Personnel who will perform the interim analyses	22
	1.4.4.2	Personnel who will have access to interim results	22
	1.4.4.3	Access control	22
	1.4.4.4	Information to be disseminated outside the AC	23
	1.4.4.5	Recipient of the recommendation	23
1.5	Softwa	re	23
1.6	Valida	tion model	23
2.	General n	nethodology	24

ARGX-113-2009

Final and Interim Analysis

1. INTRODUCTION

This statistical analysis plan (SAP) describes the interim and final statistical analyses to be performed for study ARGX-113-2009 (BE-80-2100382).

The final analysis of part A data will be performed after its last participant completes their last visit. Similarly, the final analysis of part B data will be performed after its last participant completes their last visit. Additionally, at the part B final analysis, all analyses will be performed on the pooled Part A and B data.

This SAP covers the efficacy (including participant-reported outcome [PRO] measures and quality of life [QoL]), pharmacokinetic (PK), pharmacodynamic (PD), immunogenicity, general characteristics and safety parts of the statistical analysis. It specifies the analysis displays to be presented and describes the methods and procedures in a more elaborated way than in the statistical methods section of the Clinical Study Protocol (CSP).

Analyses of exploratory endpoints or substudy endpoints are not in scope of this SAP.

The statistical analysis will process and present the results following the International Council for Harmonization (ICH) standards, in particular the ICH-E3, ICH-E6, and ICH-E9 guidelines.

[figure not shown]

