1.4 INTERIM ANALYSIS

An IA will be performed during part A of the study. Results of the IA will help supporting the sponsor's decision whether to continue part B of the study as currently designed, modify the sample size for part B, or discontinue the study (both parts A and B) due to lack of efficacy.

The IA of part A will be performed using data collected from all of its participants through the data cutoff time point (defined as the last participant in part A reaching week 26).

Both part A and part B of the study are randomized and double-blinded. Section 1.4.4 provides the measures to ensure that blinding and integrity of the part A dataset is maintained while the unblinded IA is being performed.

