2.4.3 Order in tables and listings

All tables and figures will be presented per treatment, unless specified otherwise. In by-visit displays, worst-case will be shown last, if present. All tables and figures will be presented separately for Part A, Part B and pooled Part A and B, with Part A (or B or A+B) indicated in the first title and included in output file names as _A (or _B or AB). Listings will be presented for Part A and Part B participants separately.

In listings for general characteristics, results will be ordered by treatment and participant, unless specified otherwise.

SGS	Statistical Analysis Plan	
ARGX-113-2009	Final and Interim Analysis	Final 4.0 of 04NOV2024

All other listings will be ordered by treatment, participant, analysis visit and time point, unless specified otherwise.

In tables showing several parameters, each parameter will begin on a new page and parameters will be sorted alphabetically, within the parameter category if applicable.

The Efgartigimod PH20 SC treatment group will always be shown first, then the Placebo treatment group.

SGS	Statistical Analysis Plan	
ARGX-113-2009	Final and Interim Analysis	Final 4.0 of 04NOV2024

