4.1.2.3 PRESENTATION OF RESULTS

The primary endpoint will be analyzed on the FAS population and additionally on the PP population as sensitivity analysis.

A frequency tabulation will be provided for the disease status as collected in the CRF per analysis visit. This includes the status 'CR while being off OCS therapy for at least 8 weeks'. For participants who received rescue therapy, only assessments prior to or on the start date of rescue therapy will be considered.

Frequency tabulations will be provided of the percentage of participants who are in CR while receiving efgartigimod PH20 SC or placebo and have been off OCS therapy for ≥8 weeks at week 36 (composite strategy - primary endpoint). The table will be repeated for subgroups, including treatment differences in proportions with 95% Wald CI (with continuity correction).

The proportion of participants with BP who are in CRoff at week 36 will be tested by means of a Cochran-Mantel-Haenszel (CMH) test stratified for the 2 stratification factors of disease history (newly diagnosed versus relapsing) and disease severity as per IGA-BP at screening (moderate versus severe). The common (conditional) odds ratio will be provided, along with the exact 95% CI and 2-sided p-value from the CMH association test. In addition, the Klingenberg 95% CI for the strata-adjusted difference of proportions along with its midpoint estimate will be provided. Homogeneity of the odds ratios will be tested by means of a Breslow-Day test with Tarone's adjustment.

A sensitivity analysis will be performed on this primary endpoint using exact logistic regression with fixed effect terms for randomized treatment and stratified for the 2 stratification factors of disease history and disease severity as per IGA-BP at screening. Treatment groups will be compared in terms of the (conditional) odds ratio with 95% CI. A non-linear model with fixed effect terms for randomized treatment and the 2 stratification factors will be fitted to obtain the estimated treatment difference in proportions with 95% CI.

The same CMH test as for the primary analysis will be applied for the supplementary analysis (using a treatment policy strategy).

All sensitivity and supplementary analyses for the primary endpoint will be performed both for the analysis of study Part A, study Part B and pooled study Part A and B.

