Changes from baseline in the 24-hour average itch NRS score will be analysed using a mixed-effect model for repeated measurements (MMRM). The least square means on changes from baseline at week 36 will be calculated as well at the other analysis visits (with no strict control of alpha of these). The MMRM model will include treatment by visit and baseline value by visit interaction terms, and the two stratification factors as covariates. Within-subject correlation will be modeled using the R matrix. With 13 post-baseline visits during the treatment-phase, a standard unstructured covariance matrix would require 91 variance parameters. Therefore, a modified unstructured covariance matrix (UN) will be used: ANTE(1).

Least square means, SE, and 95% 2-sided CI for placebo and efgartigimod will be reported by analysis visit, along with LS means of the between-arm difference including also with SE, 95% 2-sided CI, and 2-sided p-value. If the default Newton-Raphson algorithm used by SAS PROC MIXED fails to converge, the following will be tried to avoid lack of convergence while maintaining an unstructured variance:

The Fisher scoring algorithm (via the SCORING = 5 option of the PROC MIXED statement) will be used to obtain the initial values of covariance parameters. In the rare case where the above fails, the following covariance structures will be tested for convergence (in order): toeph, arh(1), csh, toep, ar(1) and cs).

[figure not shown]
All itch NRS data will be listed.

Subgroup tables will be created for all key secondary endpoints (not for supplementary analysis).

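### The pooled Part A+B analyses carry no term for study part: a small modelling gap that mildly shrinks the pooled odds ratio and leaves the Part B result untouched

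*SAP*

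**What the plan says.** SAP section 1 states: "Additionally, at the part B final analysis, all analyses will be performed on the pooled Part A and B data". Section 2.4.3 repeats this for displays: "All tables and figures will be presented separately for Part A, Part B and pooled Part A and B". Listings are the exception: "Listings will be presented for Part A and Part B participants separately". Section 4.1.2.3 runs the sensitivity and supplementary analyses of the primary endpoint "both for the analysis of study Part A, study Part B and pooled study Part A and B".

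The models are written once and serve all three data sets. The primary CMH test is "stratified for the 2 stratification factors of disease history (newly diagnosed versus relapsing) and disease severity as per IGA-BP at screening", and the exact logistic model uses the same two factors. In section 4.1.3.2 the NCOD ANCOVA has treatment and the stratification variables, and the itch MMRM takes "the two stratification factors as covariates" alongside its treatment-by-visit and baseline-by-visit terms. None of these names study part.

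The parts were randomised differently. Protocol section 6.3 stratifies Part B by region, then by history and severity in the rest-of-world stratum only. SAP section 4.1 says Part A was randomised without stratification and that its factors are derived for the models. SAP section 1.4 lets the Part A interim support a decision to continue, "modify the sample size for part B, or discontinue the study (both parts A and B) due to lack of efficacy".

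Protocol section 9.3.3.5 says only that pooled analyses will be done and leaves the details to the SAP. The SAP gives no pooling method, no check of consistency by part, and no statement on how pooled p-values are to be read.

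**The concern.** When two separately randomised cohorts are combined, the usual course is to compare treatments within cohort and then combine. The written pooled models compare across the merged set. Two matters follow, and they should be kept apart.

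- **Missing part term.** The odds ratio is the population-level summary in SAP section 4.1.2.1. It is non-collapsible, so merging parts with different placebo rates moves it towards 1 even when both parts share the same true value. For NCOD and itch, any difference in mean between parts goes into the residual.
- **Selection on Part A.** Pooled data exist only if the study continued after Part A's own results were seen, and the size of Part B may be raised on the same results. Part A's contribution to the pooled estimate is then somewhat favourable.

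At stake is how the pooled tables read beside the Part B tables, since both would show estimates and two-sided p-values in the same layout.

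**Working it through.** **Inputs.** Part A 40 and Part B 120, both 1:1 (SAP 1.3), so part weights are 40/160 = 0.25 and 120/160 = 0.75. Go needs the LL80 limit above 10% and the UL90 limit above 30%; Stop is UL90 at or below 30% (SAP 1.4.1.4). Illustrative rates are 20% placebo and 50% efgartigimod (SAP 1.4.2.1). Placebo rates that differ by part are assumptions; the documents give none.

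**The plan's own figure.** There is no pooled figure to reproduce. For the 120 in Part B, at 20% versus 50% the chi-square formula gives (1.960√(2·0.35·0.65) + 1.282√(0.16 + 0.25))² / 0.30² = (1.322 + 0.821)²/0.09 ≈ 51.0, so 52 per arm (104 in total). At 60 per arm power is 94.1%. This agrees with more than 90% power at 120; the protocol's own rates are blacked out.

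**Step 1: risk difference without part.** With equal arms in each part, the part weights are the same in both arms. The crude difference is then 0.25·RD_A + 0.75·RD_B, and Mantel-Haenszel weighting by part gives the same weights. Example with placebo 10% in A, 30% in B and a true odds ratio of 4 in each:
- Active rates: A 0.4444/1.4444 = 0.3077; B 1.7143/2.7143 = 0.6316.
- Stratified: 0.25·0.2077 + 0.75·0.3316 = 0.3006.
- Crude: 0.5506 − 0.2500 = 0.3006.

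**Step 2: odds ratio without part.** Same example: (0.5506/0.4494)/(0.25/0.75) = 1.225/0.333 = 3.68. Repeating for other assumed gaps, with a true value of 4.0 throughout:

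| Placebo A / B | Pooled placebo | Pooled active | Crude OR | OR stratified by part |
|---|---|---|---|---|
| 10% / 20% | 0.175 | 0.452 | 3.89 | 4.00 |
| 20% / 30% | 0.275 | 0.599 | 3.93 | 4.00 |
| 10% / 30% | 0.250 | 0.551 | 3.68 | 4.00 |
| 30% / 10% | 0.150 | 0.389 | 3.60 | 4.00 |
| 10% / 40% | 0.325 | 0.622 | 3.42 | 4.00 |

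The crude figures ignore the history and severity strata, which may absorb some of the gap.

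**Step 3: NCOD and itch.** A gap of g SD between part means adds 0.25·0.75·g² = 0.1875g² to the variance. At g = 0.3 that is 0.0169: about 1.7% on the variance and under 1% on the standard error.

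**Step 4: selection on Part A.** Part A outcomes (20 per arm) were enumerated through the decision rule, with Wald limits standing in for the Klingenberg limits (Newcombe limits agree) and placebo 20%. With Part B at 120, the pooled expectation is 0.25·E[Part A difference given continuation] + 0.75·true difference. At a true 30 given Go: 0.25·37.12 + 0.75·30 = 31.78.

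| True difference | P(Go) | Bias given Go | P(not Stop) | Bias given not Stop |
|---|---|---|---|---|
| 30 | 0.704 | +1.8 | 0.894 | +0.8 |
| 20 | 0.437 | +3.2 | 0.705 | +1.7 |
| 10 | 0.190 | +4.8 | 0.420 | +3.2 |
| 0 | 0.049 | +6.5 | 0.145 | +5.0 |

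Allowing Part B to grow to 240 changes the not-Stop value at a true 30 from +0.75 to +1.04. Simulated with a part stratum, the pooled difference given Go is the same as without it: 31.8 at a true 30 and 23.2 at a true 20.

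**Step 5: error rate under no effect (simulation).** Over all trials, pooled CMH rejects in 5.0% without part and 5.05% with it; with placebo rates of 10% and 30%, the figures are 4.5% and 5.05%. Given Go, it rejects in 14.7% without part and 14.8% with it, against 4.7% for Part B alone. Go followed by a pooled rejection occurs in about 0.049·0.147 = 0.7% of null trials.

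**The case against.** The case for leaving the plan alone is fairly strong. The two parts share eligibility criteria, schedule and conduct (Protocol 4.1.2), so a 20- or 30-point gap in placebo rates has no support in the documents; at 10 points the odds ratio loses about 0.1. The loss is conservative. The existing strata may recover some of it. Pooling sits under other analyses in the protocol, whose summary of changes gives its purpose as exploring the effect across parts, and fixed-sequence testing is confined to Part B (SAP 4.1.5). The SAS code in appendix 9.3 is not shown in the available copy, so a part term there cannot be excluded. All of this stands, and it limits the point to a minor one.

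It does not remove the point. The text names the model terms and omits part, the SAP itself never calls the pooled results exploratory, and the specified outputs include p-values.

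A reader might go further and infer that the missing term makes pooled effects wrong in either direction, or that it causes the selection inflation. The documents do not support that. With 1:1 allocation in both parts the risk difference is unaffected, and adding part leaves the inflation unchanged. Nor is the 14.7% rejection rate given Go an inflated type I error: the rate over all trials is about 5%.

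**Conclusion.** The point holds as a minor improvement to the pooled models. Omitting part leaves the pooled risk difference unbiased, shrinks a true odds ratio of 4.0 to about 3.9 at a 10-point placebo gap and to 3.6 to 3.7 at 10% versus 30% (depending on which part has the lower rate), and costs under 1% of standard error on NCOD or itch at a 0.3 SD gap. These sizes rest on assumed placebo rates and gaps, arms of equal size within each part, and no help from the existing strata.

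Selection on Part A is a separate matter of labelling. It adds roughly 1 to 2 points to the pooled difference at a true 30, and more at smaller true effects. The Go-conditional values are upper bounds: the futility rule is non-binding (Protocol 9.4.1; SAP 1.4.1.4 allows departures from it), and the interim uses a last-visit proxy for ongoing participants (SAP 1.4.1.2) whereas the pooled analysis uses final data.

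It would be wrong to conclude that the confirmatory result is compromised. Part B is analysed on its own and only Part B enters the alpha-controlled sequence. It would also be too broad to say that everything is pooled: listings are kept separate.

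**What to change.** In the pooled analyses only, add study part (A or B) as a stratum in the CMH test, the exact logistic regression and the stratified time-to-event tests, and as a factor in the ANCOVA and MMRM. Leave the Part A and Part B models as they are.

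Separately, state in the SAP and in a footnote to the pooled tables that pooled p-values are descriptive, and that Part A data informed the decisions to continue and to size Part B, so the pooled difference may be somewhat high. The part term does not deal with this; the label does.

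Cost: one more variable in the pooled code and a footnote. The statistical price is 8 strata instead of 4. Part A's 40 participants spread over 4 strata average 5 per arm, or about 1 expected placebo responder per stratum at 20%, so the planned Breslow-Day test of homogeneity becomes weak in the pooled data and should be read with that in mind.

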1.1 STUDY OBJECTIVES

1.1.1 Part A

The primary objective of part A of study 2009 is to evaluate the efficacy of Efgartigimod (EFG) PH20 SC on achieving sustained remission in the treatment of participants with Bullous Pemphigoid (BP).

The secondary objectives of Part A are:

- To evaluate the corticosteroid-sparing effects of EFG PH20 SC in participants with BP
- To characterize the overall efficacy of EFG PH20 SC in the treatment of participants with BP
- To evaluate the efficacy of EFG PH20 SC in preventing relapse of BP
- To evaluate the effect of EFG PH20 SC on pruritus in participants with BP
- To assess the safety and tolerability of EFG PH20 SC administered to participants with BP
- To assess glucocorticoid-associated morbidity and evaluate the impact of EFG PH20 SC in reduction of glucocorticoid toxicity
- To evaluate the effects of EFG PH20 SC on the QoL of participants with BP
- To evaluate the pharmacokinetics of EFG PH20 SC in participants with BP
- To evaluate the pharmacodynamics of EFG PH20 SC in participants with BP
- To evaluate the immunogenicity of EFG PH20 SC in participants with BP

 To evaluate the competency of participants or caregivers to (self-)administer EFG PH20 SC

The exploratory objectives include the following:

 To further explore the pharmacodynamics of EFG PH20 SC in participants with BP

1.1.2 Part B

[figure not shown]
According to the protocol, the primary objective of part B of study 2009 is to evaluate the efficacy of EFG PH20 SC on achieving sustained remission in the treatment of participants with BP.

The secondary objectives of Part B are:

- To evaluate the corticosteroid-sparing effects of EFG PH20 SC in participants with BP
- To characterize the overall efficacy of EFG PH20 SC in the treatment of participants with BP
- To evaluate the efficacy of EFG PH20 SC in preventing relapse of BP
- To characterize the efficacy of EFG PH20 SC in the treatment of participants with BP
- To evaluate the effect of EFG PH20 SC on pruritus in participants with BP
- To further characterize the overall efficacy of EFG PH20 SC in the treatment of participants with BP
- To assess the safety and tolerability of EFG PH20 SC administered to participants with BP
- To assess glucocorticoid-associated morbidity and evaluate the impact of EFG PH20 SC in reduction of glucocorticoid toxicity
- To evaluate the effects of EFG PH20 SC on the QoL of participants with BP
- To evaluate the pharmacokinetics of EFG PH20 SC in participants with BP
- To evaluate the pharmacodynamics of EFG PH20 SC in participants with BP
- To evaluate the immunogenicity of EFG PH20 SC in participants with BP
- To evaluate the competency of participants or caregivers to (self-)administer EFG PH20 SC

The exploratory objectives include the following:

 To further explore the pharmacodynamics of EFG PH20 SC in participants with BP

